7. STATISTICS, DATA ANALYSIS, DATA SECURITY

Data Analysis

Data will be analysed using a statistical package and platform (R Studio). Analysis will be completed by a clinical research fellow with appropriate access privileges (including honorary Imperial NHS contract) to study data.

Data Protection, Security and Compliance

This study has been reviewed and approved by the Imperial College Healthcare NHS Trust Data Protection Office (reference 20HH6360). Data and all appropriate documentation will be stored for a minimum of 10 years after the completion of the study, including the follow-up period.

All study data will be collected using a REDCap (Research Electronic Data Capture) database, with a unique study ID for each participant (only identifiable by the principal investigator using an encrypted master key held in a password protected file on NHS servers). Patients will be allocated a de-identified study ID number, derived from a key that processes NHS numbers algorithmically. This key will be kept secure in a password encrypted file (accessible only to principal investigator). Study participant data will therefore not be identifiable unless researchers revert study ID's to NHS number.

The following data (where available) will be captured by researchers from the electronic health record (EHR):

- Encrypted NHS number (master key held in password protected file on NHS server, only accessible to principal investigator)
- Age
- Ethnicity
- Comorbidities
- Classification into study group 1-3
- BNP blood test result
- Echocardiography calculated %LVEF and categorisation
- Cardiac MRI calculated EF and categorisation

Eko DUO Data Security

The only data received by Eko Health will be digital ECG data. This will not be identifiable to the patient (i.e. not associated with an NHS number, date of birth or other identifier and Eko will not have access to the key for linkage with NHS numbers). This digital ECG data is uploaded to the Eko cloud via the mobile phone app (connected to the Eko DUO by bluetooth, no data stored on the device).

The data can be freely retrieved and will only be accessed through and securely stored within Imperial College London computers and servers. At the end of the study, all digital ECG data will be retrieved from Eko's servers and stored in accordance with Imperial College London policy on secure College computers.

No ECG or other data is stored on the mobile phone/on the app.

Interim Analysis

An interim analysis will be conducted (anticipated at 3 months) when the study has recruited n = 400 patients with paired DUO-EF and echocardiography results. Based on the previous power calculation this should be sufficient to indicate with 90% power if we can reject a null hypothesis that the AUC <0.7 at the 0.05 level of significance.

Missing Data

The study design and nature of the variables collected makes missing data unlikely. In order to avoid introducing bias into the dataset by removal of participants with any missing data, all participants will be retained; missing of any variable will entail the affected participant not being included only in the analyses specifically relevant to that variable. Access to shared primary and secondary care electronic health records should make missing data retrievable in most cases. Details of any missing data will be explicitly described in any reports or publications.

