3. STUDY DESIGN & METHODS

Statistical Considerations

Type of study: Prospective cross-sectional study comparing identification of LVEF above or below 40% by DUO-EF algorithm versus gold-standard methods.

Duration: Start date 01/02/2021, duration 36 months

Number and type of participants: across all settings 2,400 total

Sample Size

Imperial College Healthcare NHS Trust performs over 20,000 echocardiograms per year across its three hospital and community sites, serving the most ethnically and socioeconomically diverse population in the UK.

Based on established data and extensive clinical expertise of the investigators, around half of all patients who attend for echocardiography at the Trust are found to have LVEF <40%. **The sample size calculation below addresses the primary objective: evaluating if the DUO-EF algorithm can achieve a performance of sensitivity and specificity above 80% for detection of LVEF above or below 40% – compared to gold-standard echocardiography.**

SAMPLE SIZE CALCULATION

Primary Variable: Left Ventricular Ejection Fraction >/< 40%

Null Hypothesis: DUO-EF **DOES NOT** detect with sensitivity and specificity exceeding 80% a LVEF greater or less than 40%

Alternate Hypothesis: DUO-EF **CAN** detect with sensitivity and specificity exceeding 80% a LVEF greater or less than 40%

Type 1 error 5% (5% 2 sided test)

Type 2 error 20% (80% power)

Based on the above parameters for sample size calculation (Ref: G*Power, proportion, difference from a constant [binomial test 1 sample test]) to address the primary objective, this study will recruit participants until at least 500 have been recruited with an LVEF above 40% and 500 with a LVEF below 40% i.e the minimum total required is 1000 patients.

This will provide us with an ability to estimate sensitivity and specificity with a 95% CI $\pm 3.3\%$, and assuming the underlying sensitivity and specificity are at least 85% provide us with 80% power at the 5 % significance level to detect that they exceed the pre-specified criterion of a sensitivity and specificity of 80%.

Dropouts: Dropouts are unlikely within the context of the primary objective since consent and the entire data collection will occur within a short space of time during a single clinical visit (standard-of-care attendance for echocardiography).

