Protocol Allowances: Although we require 466 patients with EF >40% and 466 patients with EF <40% we have rounded these up to 500 patients. Furthermore, we will likely need to recruit up to 1,500 patients in total since it is unlikely that the first 1,000 patients will fulfil the exact breakdown of required LVEF above and below 40%.

Controls: The ‘control’ population in this study are participants with LVEF>40%. Indications for referral to echocardiography are broad and include but are not limited to: suspected or known

ischaemic heart disease, suspected cardiomyopathy, pericardial disease, murmurs, assessment of valve disease, assessment of prosthetic valves, assessing chronic lung disease, neurological disease (stroke or transient ischaemic attack), arrhythmia (palpitations and/or loss of consciousness), high blood pressure (common) and as a standard investigation considered before surgery. Many of these referred patients are found to have no abnormalities on echo and are otherwise healthy. Therefore, the unselected approach of this study to include all-comers to echo will generate a population sample that can be evaluated for alignment with the type of population in whom a screening programme for heart failure may be beneficial.

Performance characteristics: Eko Health (the 'manufacturer' of the algorithm) indicate a performance of 80% sensitivity and 80% specificity for the identification of LVEF above or below 40%

Confounders: our study design precludes confounders

Avoidance of bias for primary objective

To avoid any biases in both the recording of DUO-EF readings by the member of the research team and this influencing calculation of %LVEF by the echocardiography team (sonographer), the following steps will be taken:

- The member of the research team approaching patients in the echo department for consent will not be aware of the indication for referral at time-of-consent
- DUO-EF readings can happen before or after the echo, with the member of the research team unaware of the echo-derived %LVEF until they check the electronic health record (after DUO-EF has already been recorded).
- The sonographer will not be made aware of the results of DUO-EF, therefore not biasing any interpretation of %LVEF if borderline around 40%

Study Participant Population

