Patients attending COVID-19 follow up clinic (n = 400). Only patients who are being routinely referred onto the heart failure pathway for investigations will be invited to participate i.e. patients **with clinical symptoms of heart failure**, who would/should be referred onto routine NICE pathway. Researchers will capture the point-of-care DUO-EF prediction from the Covid-19 follow up clinic setting:

- Comparing this to repeat DUO-EF ('agreement' between two time points) at time of (group 1) echocardiography
- And comparing point-of-care and time-of-echo DUO-EF results

Method for Single-Lead ECG Collection for DUO-EF

For echo and cMRI, DUO-EF recordings will be made after these gold standard investigations so as not to bias interpretation of results. The protocol for DUO-EF recording for all patients in the COVID-19 follow up clinic, GP, echo and cMRI setting will be as follows:

1. Clinical user turns on Eko DUO device and confirms connection to secure app
2. Participants sitting upright will have 15 second single-lead ECGs recorded by the Eko DUO from five different locations:
 - a. Lead I position (holding the device's electrodes between two hands)
 - b. Clavicle
 - c. Angled
 - d. V2 position
 - e. V5 position
3. Five recordings of DUO-EF recorded by researchers

The participant will be categorised as having a DUO-EF <40% if any of the five DUO-EF readings suggest this.

Data point collection: %LVEF echo, %LVEF cMRI, BNP

Recording %LVEF from echocardiography

EF is routinely measured or estimated using well-established standardized methodologies. For the purpose of this study we draw on previous work by Attia et al (2019) to record the %LVEF value on echocardiography using the first available model in a standard hierarchical sequence:

- EF determined using 3-D echocardiography¹²
- Biplane approach using the Simpson method¹³ a 2-D method, or M-mode
- In the absence of any of the preceding, the reported visually estimated EF

If the estimation is a range, the midpoint as a single LVEF value will be used. LVEF will also be classified as low ($\leq 40\%$), moderately depressed (41–49%), or normal ($\geq 50\%$).

Recording %LVEF from cardiac MRI

As with echo, standard approaches to calculating EF also exist for cMRI. Calculated %LVEF (reported as standard) will be recorded alongside classification as low ($\leq 40\%$), moderately depressed (41–49%), or normal ($\geq 50\%$).

Brain Natriuretic Peptide

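### The available-case rule takes participants with no usable DUO-EF result out of the primary accuracy analysis, so the all-comers claim rests on readable recordings only and may overstate accuracy

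*Protocol*

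**What the plan says.** Section 7 of the protocol, under Missing Data, keeps all participants in the dataset but adds that "missing of any variable will entail the affected participant not being included only in the analyses specifically relevant to that variable". The same paragraph calls missing data unlikely, expects most of it to be recoverable from electronic health records, and promises to describe it in reports. It gives no expected rate of failed recordings.

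The primary outcome (section 3.1) is the sensitivity and specificity of DUO-EF, so DUO-EF is a variable that the primary analysis needs. Section 3, under the method for single-lead ECG collection, asks for five 15-second recordings and sets the person-level rule: "The participant will be categorised as having a DUO-EF <40% if any of the five DUO-EF readings suggest this". It has no category for a recording that cannot be classified, and does not say how a participant with only some readable recordings is handled.

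The sample size text tests against the "pre-specified criterion of a sensitivity and specificity of 80" per cent, "assuming the underlying sensitivity and specificity are at least 85" per cent. Elsewhere section 3 describes the echo sample as unselected all-comers and links it to use of DUO-EF as a screening tool.

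**The concern.** This is a stated rule, not a gap left for a statistical analysis plan. For most variables an available-case rule is ordinary. For the index test of a diagnostic accuracy study it changes who the result applies to: the denominator becomes people in whom the test worked, while the claim is framed for everyone attending.

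The paragraph's safeguards do not reach this variable. DUO-EF is not among the items that section 7 lists as taken from the health record, so an unreadable recording is not obviously recoverable there. Describing missing data in the report does not alter the denominator of the primary estimate.

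What is at stake is a margin of 5 points between the assumed 85% and the 80% criterion. If people without a usable result would tend to be misclassified, or if a test that gives no answer is regarded as a failed test, leaving them out could turn a result at the criterion into an apparent success.

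**Working it through.** **Inputs from the protocol (section 3).** Criterion 0.80; assumed true value 0.85; "Type 1 error 5% (5% 2 sided test"), taken as an upper tail of 0.025; "Type 2 error 20% (80% power"); one-sample binomial test in each LVEF class; 466 per class, rounded up to 500.

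**Input assumed.** The share m of an LVEF class with no usable DUO-EF result. The protocol gives no figure, so a range is shown.

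**Step 1: reproduce the plan's figure.** With an exact binomial test of 0.80 against 0.85 at upper tail 0.025, the smallest n with at least 80% power is 466 (reject at 390 or more; actual tail 0.0245; power 0.805). This matches the protocol: "Although we require 466 patients with EF >40% and 466 patients with EF <40% we have rounded these up to 500 patients". At n = 500 the test rejects at 418 or more, with actual tail 0.0232 and power 0.827.

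**Step 2: head count is not the problem.** Going from 500 to 466 is a loss of 34/500 = 6.8%, so the rounding absorbs moderate losses. The issue is bias and what the estimate represents.

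**Step 3: accuracy over all participants in a class.** Let q be the accuracy credited to those with no usable result:

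accuracy in all = (1 − m) × 0.85 + m × q

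Setting this to 0.80 gives m = 0.05 / (0.85 − q):

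| q | m that removes the margin |
|---|---|
| 0 (all counted wrong) | 0.05/0.85 = 5.9% |
| 0.25 | 0.05/0.60 = 8.3% |
| 0.50 | 0.05/0.35 = 14.3% |
| 0.70 | 0.05/0.15 = 33% |
| 0.85 (missing at random) | none; no bias at any m |

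**Step 4: chance of beating 80% in the worst case (q = 0).** The excluded analysis uses n = 500(1 − m) with p = 0.85. The all-participants analysis uses n = 500 with p = 0.85(1 − m) and critical value 418.

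| m | Accuracy, all counted | n if excluded | Success, excluded | Success, all counted |
|---|---|---|---|---|
| 1% | 84.15% | 495 | 82% | 66% |
| 2% | 83.3% | 490 | 81% | 46% |
| 3% | 82.45% | 485 | 81% | 27% |
| 5% | 80.75% | 475 | 79% | 6% |
| 5.9% | 80.0% | 471 | 78% | 2% |

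Power of an exact test moves in a saw-tooth with n, which is why it is a little under 80% at 471 although 466 reaches it.

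**Step 5: how person-level failure relates to five recordings.** If any readable recording is enough to classify a person, a person is unusable only when all five fail. With independent failures at rate f per recording, m = f^5: f = 30% gives m = 0.24%, and m = 2% needs f of about 46%. Failures within one person are probably correlated, which raises m for a given f. If instead each recording were treated as a variable in its own right, the excluded share would be 1 − (1 − f)^5, which is 22.6% at f = 5%. The protocol does not settle which reading applies.

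**The case against.** A reader might infer that the rule inflates accuracy. The documents do not support that. They give no failure rate, do not say that the algorithm can return an unclassifiable result, and do not say in so many words that an unusable recording counts as missing. If failures are unrelated to whether the algorithm would have been right, the readable-only estimate is unbiased. Five attempts, a data collection confined to one visit, and an exclusion for features that would prevent stethoscope examination all make total failure less likely. So 5.9% is a threshold, not a forecast.

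A reader might also take the any-positive rule as a second source of inflation, because fewer readable recordings mean fewer chances of a positive call. That works in both directions: sensitivity falls and specificity rises. With an assumed 95% specificity per reading and independent readings, person-level specificity is 0.95^5 = 77% with five and 0.95^3 = 86% with three. Independence between readings from one person in one session is implausible, and the effect does not come from the Missing Data rule.

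A third temptation is to score every incomplete all-negative set as wrong. That is unsound. With 85% specificity and independent failures, specificity becomes 0.85 × (1 − f)^5, which is 80% at f = 1.2% and 76.8% at f = 2%.

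Finally, a separate analysis plan may add a suitable sensitivity analysis. It may, but it would have to supplement or override a sentence that the protocol already fixes. What stands after all this is the exclusion itself and the mismatch with the all-comers framing.

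**Conclusion.** The point holds in a limited form. Read naturally, the rule restricts the primary sensitivity and specificity to participants with a usable DUO-EF result, while the protocol presents the result for unselected attenders. Accuracy may be overstated; whether it is, and by how much, cannot be told from the protocol.

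The size is a bound resting on three assumptions: 85% accuracy among readable results, 500 participants per LVEF class, and every unusable result counted as wrong. Under these the 5-point margin is gone at about 5.9% unusable, where the excluded analysis succeeds about 78% of the time against about 2% with everyone counted. Milder assumptions move the threshold to 14.3% or beyond, and missingness at random removes the problem.

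**What to change.** In the Missing Data paragraph, exempt the index test from the available-case rule and define an unusable DUO-EF result. Then:

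- Keep the readable-only analysis, and add beside it an intention-to-diagnose sensitivity analysis. A participant with no classifiable recording counts as a false negative if LVEF is low and as a false positive otherwise. Label it as a worst-case bound.
- Report the unusable rate by LVEF class.
- In the recording method, state that participants with some readable recordings are classified by the any-positive rule on those recordings. Report how many recordings were readable, and repeat the analysis in those with all five. Do not score incomplete all-negative sets as wrong.

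The cost is a few sentences and one extra table, with no added participants or procedures. The downside is a possibly less favourable secondary accuracy figure.

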8. REGULATORY ISSUES

8.1 ETHICS APPROVAL

The Study Coordination Centre has obtained approval from the **xxx** Research Ethics Committee (REC) and Health Research Authority (HRA). The study must also receive confirmation of capacity and capability from each participating NHS Trust before accepting participants into the study or any research activity is carried out. The study will be conducted in accordance with the recommendations for physicians involved in research on human subjects adopted by the 18th World Medical Assembly, Helsinki 1964 and later revisions.

8.2 CONSENT

Consent to enter the study will be sought from each participant only after a full explanation has been given, an information leaflet offered and time allowed for consideration. The right of the participant to refuse to participate without giving reasons will be respected.

Consent will either be in the form of a standard paper consent form or, for those with access to the Imperial NHS Care Information Exchange electronic patient record, using a digital consent form that conforms to the HRA and MHRA's [joint statement](#) on e-consent for research.

After the participant has entered the study the clinician remains free to give alternative treatment to that specified in the protocol at any stage if he/she feels it is in the participant's best interest, but the reasons for doing so should be recorded. In these cases the participants remain within the study for the purposes of follow-up and data analysis. All participants are free to withdraw at any time from the protocol treatment without giving reasons and without prejudicing further treatment.

8.3 CONFIDENTIALITY

The Chief Investigator will preserve the confidentiality of participants taking part in the study and is registered under the Data Protection Act.

8.4 INDEMNITY

Imperial College London holds negligent harm and non-negligent harm insurance policies which apply to this study.

8.5 SPONSOR

Imperial College London will act as the main Sponsor for this study. Delegated responsibilities will be assigned to the NHS trusts taking part in this study.

8.6 FUNDING

NIHR is funding this study. Participants will not be paid for joining the study. Investigators will receive no direct or indirect payments for conducting the study.

8.7 AUDITS

The study may be subject to inspection and audit by Imperial College London under their remit as sponsor and other regulatory bodies to ensure adherence to GCP and the UK Policy Framework for Health and Social Care Research.

9. STUDY MANAGEMENT

The day-to-day management of the study will be co-ordinated through the Imperial College & Trust Connected Care Bureau, [name].

10. PUBLICATION POLICY

Results from this study will be published in peer-reviewed journals and presented at relevant conferences with all named lead and co-investigators as authors.

Appendix 1. Summary of investigations, treatment and assessments

Exam	Week of Treatment			
	Pre-treatment	Group 1	Group 2	Group 3
Initial/repeat (for GP and COVID-19 follow up patients) DUO-EF reading at echocardiography/cMRI	Nil	X	X	X

Initial DUO-EF reading in COVID-19 clinic or with GP	Nil		X	X
24 month follow-up phone call for DUO-EF positive but gold standard negative	Nil	X	X	X
